12.1.2 Serious Adverse Event or Serious Adverse Drug Reaction

As per ICH-GCP (E6, R2), ICMR and Indian GCP guidelines, serious adverse event (SAE) or serious adverse drug reaction is any medical occurrence that at any dose:

No.	Description
1	Results in death
2	Is life threatening
3	Requires inpatient hospitalization or prolongation of existing hospitalization
4	Results in persistent or significant disability/incapacity
5	is a congenital anomaly or birth defect
6	Requirement of intervention to prevent permanent impairment or damage

Any other important medical event that may not result in death, or is life threatening, or require hospitalization, may be considered a SAE when, based upon appropriate medical judgment, the event may jeopardize the subject and may require medical or surgical intervention to prevent one of the outcomes listed above. Examples of such medical events include allergic broncho-spasm requiring intensive treatment in an emergency room or at home, blood dyscarsias or convulsions that do not result in inpatient hospitalization, or the development of drug dependency or drug abuse.

All SAEs will be recorded on the appropriate SAE form.

12.1.3 Abnormal Laboratory Values or Abnormal Clinical Findings

Laboratory abnormalities that constitute an Adverse event in their own right (are considered clinically significant, induce clinical signs or symptoms, require concomitant therapy or require changes in study treatment), should be recorded on the Adverse Events CRF. Abnormal laboratory values or abnormal clinical findings at the time of screening will be considered as medical history and not AE. Whenever possible, a diagnosis, rather than a symptom should be provided (e.g. anemia instead of low hemoglobin). Laboratory abnormalities that meet the criteria for Adverse Events should be followed until they have

CONFIDENTIAL

Page 57 of 74

Ipca Laboratories Ltd Version 1.0 (Amendment 3.0)

returned to normal or an adequate explanation of the abnormality is found. When an abnormal laboratory or test result corresponds to a sign/symptom of an already reported adverse event, it is not necessary to separately record the lab/test result as an additional event.

Abnormal lab values observed during study or in post study safety analysis should be reported as an adverse event if-

- The test result is accompanied by an associated symptom or clinical sign.
- The test result requires an additional diagnostic exam or medical/surgical intervention.
- The test result leads to a change in the study drug dose or study discontinuation, introduction of a significant concomitant drug treatment or other therapy.
- The test result is considered by the principal investigator/clinical investigator or by the sponsor as an adverse event.

12.2 ADVERSE EVENT DOCUMENTATION

All adverse events that are reported will be properly documented on the adverse event reporting form. In particular the information required will include: a full description of the event, date and time of onset, date and time of dosing, description of the severity of the event, any treatment or diagnostic steps taken in relation to the event, description of the outcome of the event, judgment by the physician of any relationship of the event to the Investigational Product or procedures.

A summary of the recorded adverse events capturing all the necessary details will be forwarded to the sponsor's pharmacovigilance department at [contact] on resolution of the adverse event.

12.3 REPORTING OF SERIOUS ADVERSE EVENTS

All the serious adverse events should be reported by Investigator to the Ethics Committee and through CBCC Global Research LLP to the CLA and the Sponsor or his representative within 24.00 hours of their occurrence. The report of SAE of death after due analysis to be forwarded within 14 days of occurrence. The reporting of SAE from investigator and sponsor shall be done as per New Drugs and Clinical Trials Rules 2019 as tabled below.

Reporting SAE (including permanent disability or any other injury other than death)						
Particular	From	To	Timelines			
Initial	Investigator	CLA, Sponsor / its	24 hr of occurrence			
		Representative, EC				
With Due Analysis	Investigator	CLA, Chairperson of EC, Head of	14 days of reporting			
		Institute				
With Due Analysis	Sponsor / its	CLA, Chairperson of EC, Head of	14 days of reporting			
	Representative	Institute				

CONFIDENTIAL

Page 58 of 74

Ipca Laboratories Ltd Version 1.0 (Amendment 3.0)

Reporting SAE (Death)						
Particular	From	To	Timeline			
Initial	Investigator	CLA, Sponsor / its	24 hr of occurrence			
	_	Representative, EC				
With Due Analysis	Investigator	CLA, Head of Institute	14 days of knowledge of			
_	_		occurrence			
With Due Analysis	Sponsor / its	CLA, Head of Institute	14 days of knowledge of			
	Representative		occurrence			

In case the Investigator fails to report any serious adverse event with in the stipulated period, he shall have to furnish the reason for the delay to the satisfaction of the CLA along with the report of the serious adverse event.

12.4 DCGI NOTIFICATION

CBCC Global Research LLP on behalf of sponsor shall notify the DCGI, by submission of any SAE(s) [as per regulatory requirement of India] associated with the use of the drug as soon as possible but not later than 14 days.

The Investigator will report all serious adverse events (including death, irrespective of the reason) to the applicable local regulatory authority, Sponsor, Ethics Committee and Head of institution within 24 hours of occurrence. The notification to the applicable local regulatory authority, Sponsor, Independent Ethics Committee and Head of institution has to be followed by a serious adverse event report (including death, irrespective of the reason) as per the required timelines of applicable regulatory requirements. The Sponsor and Ethics Committee will inform to the applicable regulatory authorities as per the required timelines, as applicable. The written report will include a detailed description of the observed symptoms, laboratory tests and treatment of the event. Subject demographic information, subject history, concomitant medication and date/time of occurrence and report of the event must also be clearly stated. The Investigator will judge the possible causal relationship between the event and the investigational medicinal product. The study may be suspended or terminated depending on the seriousness of the adverse effects encountered during the study.

12.5 EXPOSURE IN UTERO DURING CLINICAL STUDIES

If a subject becomes pregnant during study then she will be discontinued from the study and will be followed until the outcome of the pregnancy is known (e.g., delivery, elective termination, or spontaneous abortion). If subject becomes pregnant within 07 days after administration of last dose of study medication will be followed until the outcome of the pregnancy is known (e.g., delivery elective termination, or spontaneous abortion). The investigator should make every effort to follow the subject until completion of the pregnancy. The Investigator must notify sponsor and ethics committee within 24.00 hours of first identification of the occurrence of pregnancy. Although pregnancy is not technically an AE or SAE, if the outcome of pregnancy meets the criteria for immediate classification as a SAE i.e., post-partum complication, spontaneous abortion, stillbirth, neonatal death, or congenital anomaly,

Page 59 of 74

Ipca Laboratories Ltd Version 1.0 (Amendment 3.0)

including that in an aborted foetus, the investigator will follow the procedure for reporting SAEs.

CONFIDENTIAL

Page 60 of 74

Ipca Laboratories Ltd Version 1.0 (Amendment 3.0)

13 BIOANALYTICAL PROCEDURES

Plasma samples will be assayed by a validated LCMS/MS method developed at Cliantha Research, Ahmedabad, which is specific for the determination of Clopidogrel, AT -10 (2-oxo-clopidogrel) and its metabolite MP-H4.

All available samples will be analyzed. Concentration values of the subject withdrawn/dropped out will be presented in a separate table. All concentration values below the limit of quantification will be set to zero for all pharmacokinetic and statistical evaluation. However, the concentration below the limit of quantification will be reported as Below Limit of Quantification (BLQ) in the concentration table. Any missing sample will be reported as "M" and Non-reportable concentration values will be reported as "NRV".

The criteria for repeat analysis, as defined in the respective in-house procedure will be followed. Incurred sample reanalysis will be performed as per Cliantha Research, Ahmedabad, In-house SOP standard).

Ipca Laboratories Ltd Version 1.0 (Amendment 3.0)

14 DATA HANDLING AND DATA ANALYSIS

14.1 SOURCE DOCUMENTS

Source data are all information, original records of clinical findings, observations, or other activities in a clinical study necessary for the reconstruction and evaluation of the study. Source data are contained in source documents. Examples of these original documents and data records include, but are not limited to, clinical pharmacology records, clinical and office charts, laboratory notes, memoranda, patient's memory aid (diaries) or evaluation checklists, pharmacy dispensing records, recorded data from automated instruments, copies or transcriptions certified after verification as being accurate and complete, microfiches, photographic negatives, microfilm or magnetic media, X-rays, and patient files and records kept at the pharmacy, laboratories and medico-technical departments involved in the clinical study.

The study site will maintain appropriate medical and research records for this study, in compliance with ICH E6 guidelines and Indian GCP guidelines along with the regulatory and institutional requirements for the protection of confidentiality of subject. Sponsor and EC will have access to records. The study site will permit authorized representatives of the sponsor(s), EC and regulatory agencies to examine (and when required by applicable law, to copy) clinical records for the purposes of quality assurance reviews, audits, and evaluation of the study safety and progress.

14.2 DATA COLLECTION

Study specific paper case record form (CRF) will be designed by CBCC Global Research LLP and used to document the subject's data during the course of the study. The investigator will ensure that all data are entered promptly, legibly, completely and accurately. The CRF along with subjects 12-lead ECG recording, chest X-ray (PA view), lab reports etc. will serve as source documents.

14.3 PHARMACOKINETIC PARAMETERS AND ANALYSIS

Pharmacokinetic parameters (AUCt, AUCinf, Cmax, tmax, t½, kel, Cl/F, Vd/F) will be estimated following noncompartmental analysis of plasma concentration time-course data for Clopidogrel, AT -10 (2-oxo-clopidogrel), and MP-H4. PK parameters at steady-state will be estimated for Clopidogrel, AT - 10(2-oxo-clopidogrel), and MP-H4. Statistical comparison of the single-dose and multiple-dose PK parameters of peak (Cmax) and total (AUCt, AUCinf) exposure for the AT-10 and MP-H4 will be made between the AT-10 and Clopidogrel dose groups; between and within metabolizer groups. Additionally, geometric means will be calculated for AUCt, AUCinf, and Cmax. Analyses of variance (ANOVA) will be performed on the ln-transformed PK parameters AUCt, AUCinf, and Cmax. Each ANOVA will include calculation of least-squares means (LSMs), the differences between adjusted means, and the standard error associated with these differences. Ratios of means will be calculated using the LSM for Lntransformed AUCt, AUCinf, and Cmax. Although this is not a bioequivalence study, statistical comparison of the PK of AT-10 and MP-H4 between the AT-10 and Clopidogrel dose groups will be performed.

CONFIDENTIAL

Page 62 of 74

Although this is not a bioequivalence study following PK comparison will be made:

- PK comparisons will be made for AT -10 and MP-H4 from AT -10 treatment in extensive metabolizers versus Clopidogrel treatment in extensive metabolizers
- PK comparisons will be made for AT -10 and MP-H4 from AT -10 treatment in poor metabolizers versus Clopidogrel treatment in poor metabolizers
- PK comparisons will be made for AT -10 and MP-H4 from AT -10 treatments in extensive metabolizers versus AT -10 treatments in poor metabolizers.

The 90% confidence interval of the relative mean (geometric least square mean) of AT -10 and MP-H4 from AT -10 treatment versus Clopidogrel treatment for Ln-transformed Pharmacokinetic parameters Cmax, AUCt, AUC(0-inf) will be computed. Other PK comparison will be made if deemed appropriate.

C _{max}	Maximum measured plasma concentration over the time span specified		
T _{max}	Time of the maximum measured plasma concentration. If the maximum		
	value occurs at more than one time point, T _{max} is defined as the first time		
	point with this value		
AUC _{0-t}	Area under the concentration-time curve from time zero to the last sample		
	with quantifiable concentration calculated using the linear trapezoidal		
	method		
AUC _{0-inf}	Total area under the concentration-time curve from time zero extrapolated		
	to infinity		
t _{1/2}	The terminal elimination half-life calculated by ln2/Kel		
K _{el}	The elimination rate constant		
%	It is the percentage of extrapolated area under the plasma concentration		
AUC_Extrapolation			
	be calculated as		
	$\{(AUC_{0-inf} - AUC_{0-t}) / AUC_{0-inf}\} X 100$		

Actual time of blood sample collection will be used for pharmacokinetic calculation. All concentration values below the Limit of Quantification (LOQ) will be set to "zero" for all pharmacokinetic and statistical calculations. Any missing concentration will be reported as "Missing" and will not be included for pharmacokinetic and statistical analysis.

14.4 PHARMACODYNAMIC EFFECT ANALYSIS

ADP induced platelet aggregation will be assessed for change from baseline in each treatment group at each time point assessed on each dosing day (0.5, 2 and 6 hours post dose) and 24 hrs post dosing of last dosing day in each period. The change over time for each parameter will also be assessed.

Platelet inhibition will be calculated as per below formula.

Platelet Inhibition = $(1 - \text{Residual Impedance} / \text{Baseline Impedance}) \times 100$

The results will be reported as either residual platelet aggregation, measured as maximal amplitude of impedance (ohms), or platelet inhibition. The data from treatment groups 1 and 3 will be combined in the CONFIDENTIAL Page 63 of 74

analysis and similarly for treatment group 2 and 4 will be combined in the analysis. Statistical comparison will be made between the change from baseline at each time point between the treatment groups 1 and 3 (extensive metabolizers) versus treatment groups 2 and 4 (poor metabolizers) for each treatment (AT -10 and Clopidogrel). If applicable, as clinical phase of study will be conducted in group of volunteers not more than 18, volunteer group effect will also be analyzed statistically.

The incidence of signs of bleeding from the abbreviated physical examination and the incidence of abnormal liver function tests (ALT, AST, total bilirubin, and alkaline phosphatase) will be tabulated for the treatment groups. The incidence of these events will not be formally tested and the comparison will be observational only. The observational comparisons will be made between the AT -10 and Clopidogrel in the extensive metabolizers and poor metabolizers.

Additionally, the relationship between the PK of MP-H4 and pharmacodynamic measurements will be addressed using population PK-PD analysis.

CONFIDENTIAL

Page 64 of 74

Ipca Laboratories Ltd Version 1.0 (Amendment 3.0)

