9.2.2 INVESTIGATIONAL PRODUCT ADMINISTRATION

The randomization will be generated of #40 subjects for each type of metabolizers i.e. extensive and poor, and it will be for each gender group i.e. #20 for each male and female respectively for each type of metabolizers. Total 04 randomization schedule will be prepared. Each randomization schedule should be containing 20 subjects (10 subjects for each sequence). This randomization approach will help in achieving near to equal proportionate distribution of the treatment across the study and between the gender.

CONFIDENTIAL

Page 44 of 74

Ipca Laboratories Ltd Version 1.0 (Amendment 3.0)

As per randomization, IP will be administered as per below scheme on day 1, 2, 3, 4, 5 and 6 in each period. Subjects will be fasting overnight for at least 10.00 hours before IP administration. IP will be administered orally in sitting posture with 240 ± 2 mL of water at room temperature.

Group &	Period 1	Period 2
Sequence		
Group 1	AT -10 40mg on Day 1	Clopidogrel 300 mg on Day 1
(n=10, extensive	AT -10 10 mg on Days, 2, 3, 4, 5 & 6	Clopidogrel 75 mg on Days 2, 3, 4, 5
metabolizers)		& 6
Sequence 1		
Group 2	AT -10 40 mg on Day 1	Clopidogrel 300 mg on Day 1
(n=10, poor	AT -10 10 mg on Days, 2, 3, 4, 5, & 6	Clopidogrel 75 mg on Days 2, 3, 4, 5
metabolizers)		& 6
Sequence 1		
Group 3	Clopidogrel 300 mg on Day 1	AT -10 40 mg on Day 1
(n=10, extensive	Clopidogrel 75 mg on Days 2, 3, 4, 5,	AT -10 10 mg on Days 2, 3, 4, 5 & 6
metabolizers)	& 6	
Sequence 2		
Group 4	Clopidogrel 300 mg on Day 1	AT -10 40 mg on Day 1
(n=10, poor	Clopidogrel 75 mg on Days 2, 3, 4, 5,	AT -10 10 mg on Days 2, 3, 4, 5 & 6
metabolizers)	& 6	
Sequence 2		

Note: In all the periods, IP administration will be done by trained study personnel delegated by the investigator and will be reviewed by quality control / quality assurance personnel. Investigator will be available at site during IP administration. Subjects will be asked to swallow the tablet as a whole without being chewed, crushed or bitten. The time of dosing on Day 01 will be the reference time for all subsequent dosing. Dose 02 to Dose 06 will be administered at an interval of 24 hours of previous dose.

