11.2 PHARMACODYNAMIC EFFECT ASSESSMENTS

Pharmacodynamic effect will be assessed by whole blood impedance or optical platelet aggregometry using ADP as an agonist. Blood sample for aggregometry will be collected at pre-dose and at 0.5, 2, 6 hr of IP administration on day 1 to 6 (both periods) and additionally at 24 hrs post dose sample on last dosing day of each period in sodium citrate tube. The pre-dose (0.0 hour) blood sample shall be taken within 45 minutes prior to dosing on each dosing day in each period. Blood samples will be collected as per procedure similar to pharmacokinetic blood sample collection (section 9.2.6 Pharmacokinetic Blood Sample Collection). (Note: The blood samples for aggregometry will be analyzed at the site.)

For aggregometry, 2.7 mL blood sample will be collected and processed. Preferably, the blood should be drawn with a minimum of trauma or stasis at the venipuncture site and preferred needle size is between 19 and 21 gauge.

Aggregometry will be carried-out after stimulation with 20 µM of ADP. All analyses will be performed by trained personnel. Aggregation curves will be recorded and analyzed.

Ipca Laboratories Ltd Version 1.0 (Amendment 3.0)

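### The formal platelet-aggregation comparison (extensive vs poor metabolizers within each drug) is set on change from baseline with sequences combined, and names no baseline covariate and no sequence or period term

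*Protocol*

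**What the plan says.** Section 14.4 sets the quantity, the contrast and the grouping. The quantity is change from baseline, with percent inhibition as an alternative way to report ("Platelet inhibition will be calculated as per below formula", namely one minus residual over baseline impedance, times 100). The contrast is "Statistical comparison will be made between the change from baseline at each time point between the treatment groups 1 and 3" "versus treatment groups 2 and 4 (poor metabolizers) for each treatment (AT -10 and Clopidogrel"). On grouping, "The data from treatment groups 1 and 3 will be combined in the" analysis, and groups 2 and 4 likewise. One further factor is mentioned: where applicable, because the clinic runs in batches of at most 18, "volunteer group effect will also be analyzed statistically". The synopsis repeats the change-from-baseline comparison and the combining of groups.

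No baseline covariate, sequence term or period term is named, and baseline is not defined. Section 11.2 provides several candidates: "Blood sample for aggregometry will be collected at pre-dose and at 0.5, 2, 6 hr of IP administration" on Days 1 to 6 of both periods.

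Section 7.1 allocates the 20 subjects of each genotype 1:1 to the two sequences and does not replace those who leave. Section 9.2.2 adds schedules by genotype and gender: "Each randomization schedule should be containing 20 subjects (10 subjects for each sequence"). Section 8 says that the sample size does not come from a calculation of PD effect.

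**The concern.** If the comparison is run as the sentence reads, the drug-free aggregation value is used only by subtraction. That fixes the slope of post-dose on pre-dose aggregation at 1, whatever the data show. The measurement error of the baseline reading then enters every change score that uses it. If the true slope is below 1, a chance difference in baseline between the two genotype groups also carries over into the reported genotype difference.

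Within one drug, sequence and period are the same thing: Groups 1 and 2 take AT-10 in Period 1, Groups 3 and 4 in Period 2. If aggregation drifts between periods and no term absorbs the drift, it goes into the residual variance. With 20 subjects per genotype and no replacement, precision cannot be recovered by enrolling more. What is at stake is the width of the confidence intervals for the extensive-minus-poor difference, using data that are collected anyway.

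**Working it through.** **Plan's own figure.** There is none to reproduce. The protocol gives no PD power, effect size, SD, alpha or pre/post correlation.

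**Inputs from the protocol.** 20 per genotype, 10:10 to sequence (section 7.1); change from baseline as the metric (section 14.4).

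**Assumed inputs.** Pre/post correlation rho from 0.3 to 0.9; equal pre- and post-dose SDs unless stated; two-sided alpha 0.05; period shifts of 0.25 to 1 SD of the analysed variable; equal drug-free means in the two genotypes.

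**Step 1: change score vs baseline adjustment.** With a common SD of 1,
- variance of change = 2(1 − rho)
- residual variance after adjustment = 1 − rho²
- ratio = (1 + rho)/2, multiplied by about 1 + 1/(2×20 − 4) = 1.028 for estimating the slope.

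The detectable difference is (1.96 + 0.84) × √(2 × variance/20), with the 1.028 factor included for the adjusted analysis. The last column uses the noncentral t. It takes the effect that the change score detects with 80% power (0.909 SD of the change score) and gives the adjusted power for that effect.

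| rho | (1+rho)/2 | with slope cost | detectable difference, change vs adjusted (SD) | adjusted power |
|---|---|---|---|---|
| 0.3 | 0.65 | 0.67 | 1.05 vs 0.86 | 0.93 |
| 0.5 | 0.75 | 0.77 | 0.89 vs 0.78 | 0.89 |
| 0.7 | 0.85 | 0.87 | 0.69 vs 0.64 | 0.85 |
| 0.9 | 0.95 | 0.98 | 0.40 vs 0.39 | 0.81 |

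A simulation of 4,000 trials per setting, with no period shift, gave variance ratios of 0.67, 0.77, 0.87 and 0.985. Both estimators were centred on the true value.

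**Step 2: where the gain disappears.** Let k be baseline SD over post-dose SD. The ratio becomes (1 − rho²)/(k² + 1 − 2·rho·k), before slope cost. At k = 0.75 and rho = 0.7 the true slope is 0.7/0.75 = 0.93 and the ratio is 0.51/0.5125 = 0.995. The slope cost takes it to about 1.02, and power is about 0.79 against 0.80. That loss of about one point is the worst case, reached as the slope approaches 1.

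**Step 3: omitted period shift.** With sequences 10:10 within each genotype, a shift of d SD adds d²/4 to the variance: 1.6% at 0.25, 6% at 0.5 and 25% at 1.0. Both genotypes carry the same half of the shift, so the contrast is not biased.

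**Step 4: if balance is lost.** Suppose one genotype ends at 8:10. The shares in one sequence are then 10/18 = 0.556 and 10/20 = 0.500, and 0.056 of any period shift enters the contrast. Balance is not guaranteed, because leavers are not replaced. In addition, four schedules of 20 give 80 places for 40 subjects, so they may be only partly used.

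**Step 5: which value can serve as baseline.** Section 5 describes the platelet effect as irreversible, lasting the platelet's remaining life of about 7 to 10 days. Pre-dose values on Days 2 to 6 are therefore on-drug. The Day 1 pre-dose value is the drug-free one in each period; Period 2 follows a washout of at least 14 days.

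**The case against.** The strongest reply is that section 14.4 names a metric and no model. Change from baseline can itself be regressed on baseline, and the adjusted group difference is then identical to that from modelling the post-dose value. Combining Groups 1 and 3 puts both sequences of a genotype in one analysis, as a crossover needs, and excludes no sequence term. The PK section is similarly brief: it says "Analyses of variance (ANOVA) will be performed on the ln-transformed PK parameters AUCt, AUCinf, and Cmax" without listing sequence or period. Model terms often wait for the SAP, which is not shown.

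Much of this stands. A reader might infer that the protocol prescribes an unadjusted test on one defined baseline. It says neither: adjustment is not mentioned, and baseline is undefined. A reader might also infer that combining the sequences biases the result. With 10:10 allocation it does not. Nor is any planned power lost, since none was planned.

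It is also fair that genotype is not randomised. Equal drug-free means are plausible, since the protocol has CYP2C19 acting by activating the prodrug, but the protocol does not state them.

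What does not stand is that nothing was chosen. Section 14.4 and the synopsis go as far as the tested quantity and the grouping, and section 14.4 adds one nuisance factor. It leaves out the two terms that the design makes available at almost no cost. Naming them improves a stated method.

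**Conclusion.** The point holds as an improvement to a stated method. As written, the comparison leads naturally to a change-score test, which is usually less precise than an adjusted one. Under equal SDs, adjustment would cut the variance by about 33%, 23%, 13% and 2% at rho 0.3, 0.5, 0.7 and 0.9. It can cost about one power point when the slope is near 1. A sequence term protects against a variance inflation of 6% or 25% for period shifts of 0.5 or 1.0 SD, and against a small leak if sequences become unbalanced. All of these sizes rest on assumed correlations, SD ratios, alpha and shifts; the direction does not depend on their exact values, apart from the slope-near-1 case.

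A reader might take this for the primary platelet comparison. It is not. The objective in section 6.1 is AT-10 against clopidogrel in poor and in extensive metabolizers, whereas the sentence in section 14.4 compares genotypes within a drug. Adjusting the latter does not serve the former.

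**What to change.** In section 14.4 and the synopsis:

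- Define baseline as the Day 1 pre-dose aggregation value of the same period.
- Analyse aggregation at each time point, separately for each drug, in a linear model with that baseline as covariate and with genotype, sequence (equal to period within a drug) and the volunteer-group term already planned. Either the residual value or the change may be the response, since the adjusted contrast is the same.
- Report the adjusted extensive-minus-poor difference with its confidence interval for each drug. Percent inhibition can still be reported.
- State that the adjustment assumes the two genotypes share the same drug-free mean aggregation.
- Do not label this contrast primary.

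The cost is wording, plus about two model degrees of freedom (38 to 36 before the volunteer-group term). No sample or visit is added.
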